Aim 2c - We hypothesize that lower levels of putative BRMs (neutral lipids, sCD40L, CCL5, RBC-MPs, CFH) in transfused RBC components (and in the RBC recipient) will be associated reduced levels of lung injury biomarkers and an attenuated cardiopulmonary response to RBC transfusion.

AIM 3: *To evaluate the impact of point-of-care washing of allogeneic LR-RBCs on recipient clinical outcomes.*

Aim 3a: We hypothesize that compared to standard-issue RBCs, point-of-care washed RBCs are associated with improved clinical outcomes (shorter duration of mechanical ventilation, oxygen supplementation, and ICU stay; improved oxygenation; and improved organ function).

Our large and accessible at-risk population, established clinical trial infrastructure, and multidisciplinary experience/expertise in translational, patient-centered transfusion research will assure this proposal's success.

[figure not shown]
B. RESEARCH STRATEGY

B1. SIGNIFICANCE

Problem statement: Transfusion-related pulmonary complications are the leading cause of serious transfusion-related adverse events. Transfusion-Related Acute Lung Injury (TRALI) remains the leading cause of transfusion-related death in the US and although seemingly less appreciated, Transfusion-Associated Circulatory Overload (TACO) has been the second leading cause of transfusion-related death over the past 5 years.¹ In addition to their associated mortality, both syndromes result in substantial resource utilization and associated health care cost. The majority of patients who develop TRALI will require intensive care unit (ICU) admission and ventilator support, which typically lasts from 3 to 10 days.^{23,24} Clinical evidence also notes that up to 21% of TACO cases are life-threatening and associated with increased lengths of ICU and hospital stay.²⁵⁻²⁷ Although specific preventative strategies have dramatically reduced the incidence of plasma-associated TRALI (e.g. male-only plasma donation), no prevention strategies exist for RBC-associated TRALI or TACO. Indeed, **the lack of safe and feasible strategies that can mitigate risk of RBC-associated TRALI and TACO represent critical knowledge gaps in transfusion medicine.**

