Blinding: In light of the time-sensitive, point-of-care nature of the intervention being proposed, the patient, clinical team, and members of the study team involved in the RBC washing procedure will not be blinded to the patient’s treatment allocation status. Blinding will be ensured for Drs. [name] and [name] who will be running the proposed biomarker analyses.

Other aspects of care: ARDSnet trials have demonstrated the benefit of standardizing clinical processes in ICU trials.^{75,76} In this study, clinical care that may affect development of respiratory dysfunction and associated outcomes will be standardized to the extent possible. To this end, our protocol will specify optimal ventilator strategies for both the OR and ICU environments (tidal volume \leq 8 mL/kg predicted body weight; peak inspiratory pressures $<$ 35 cm H₂O, PEEP \geq 5 cm while ventilated in the ICU). Similarly, although we will not pre-specify RBC transfusion thresholds in this protocol, we will advise restrictive transfusion practices in the postoperative period (hemoglobin target $>$ 8 g/dL in the absence of acute bleeding and/or ischemia). This transfusion threshold was chosen as it is the current standard of care at the two participating institutions. Standardization of best practices in at-risk patients will decrease the heterogeneity of the risk modifiers that may otherwise confound our associations of interest (RBC washing and intermediate markers of respiratory outcomes). Additionally, each center has adopted protocols on daily spontaneous awakening and spontaneous breathing trials to facilitate standardized weaning from ventilators (see attached appendix for specific protocols). Non-intubated patients will undergo standard titration of oxygen twice daily (at 0700 and 1900, +/- 2 hours). Patients saturating 92% or greater on room air will not receive supplemental oxygen, unless specifically requested by the primary service. If the primary care service requests oxygen supplementation for a patient saturating greater than or equal to 92% on room air, the reason for the deviation from oxygen weaning will be documented. Patients will continue to undergo evaluation for oxygen titration until liberation from oxygen therapy for 24 hours, hospital day 28, or hospital discharge, whichever comes first.

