Specific Aim 3: To facilitate the design and conduct of future clinical trials, we will also pursue a number of exploratory clinical outcomes. **The clinical outcome measure of interest for aim 3** is the duration of postoperative mechanical ventilation. Study coordinators will collect data daily until endotracheal extubation, death or hospital discharge regarding the need for mechanical ventilation. The primary clinical outcome will then be determined by calculating the duration of mechanical ventilation in hours for each study participant, determined by subtracting the time of ICU admission from the time of endotracheal extubation. If the study participant is extubated prior to ICU admission, the duration of mechanical ventilation will be assigned as 0 hours. Recognizing the potential for early death (intraoperative or early postoperative) biasing our primary clinical outcome, the number of ventilator free days (VFD) at postoperative day 28 will also be determined. Those who die prior to day 28 will be determined to have had 0 VFD. Those who are discharged from the hospital alive prior to day 28 will be assumed to have had no additional days of mechanical ventilation following hospital discharge. Additional secondary outcomes for Aim 3 will include evaluations of hypoxemia (SpO_2 , PaO_2/FiO_2), duration of oxygen supplementation, sequential organ failure assessment scores, and durations of ICU and hospital stay. The clinical diagnoses of TRALI, possible TRALI, and/or TACO will be measured through study day 5, or hospital discharge, whichever comes first.

Specimen Handling and Laboratory Assays: Aim 1b: 5 ml of blood will be drawn from each study participant at baseline, following the first RBC unit administered, 6 hours after the end of the first RBC transfusion, 18 hours after the end of first RBC transfusion, and on hospital day 5 if the patient remains hospitalized (see **Specific Aim 1** and **Specific Aim 2** for more details on the timing of blood draws). These safety laboratory

Table 6. Physiologic parameters to be measured during the study intervention period.	
Respiratory Variables	Hemodynamic Variables
PaO_2 , SpO_2 , FiO_2	Mean arterial pressure
Tidal Volume	Heart Rate
Peak inspiratory pressure	Cardiac output
Plateau airway pressure	Central venous/right atrial pressure
Positive end-expiratory pressure	Pulmonary artery wedge pressure

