Aim 3 will utilize standard analytical measures for comparing randomized treatment groups with ITT. For data that may be skewed (e.g., length of ventilation, ICU stay), Wilcoxon rank sum tests will be used to compare groups. Serial measurements (oxygen saturation) will be analyzed using longitudinal summary statistics (e.g., AUC, mean value). It should be noted that the intermediate clinical outcomes are not being powered for in this study. Estimates of precision (confidence intervals) along with range of responses will be used to guide subsequent trial designs (e.g. a larger phase II/III trial with clinical outcomes as the primary outcome of interest).

Additional statistical considerations: Consistent with early phase clinical trials, we have selected a level of significance higher than the traditional 0.05. This will facilitate advancement of the technique should it prove feasible and demonstrates potential efficacy. It is noted that multiple testing may increase the overall family wise error rate, so further research, particularly with clinical events, will be needed to quantify clinical efficacy of the approach. Missing data is expected to be minimal during the course of the study given the close surveillance the surgical and ICU environment provides. Missing specimens may occur in the event of patient discharge, death or administrative issues. Initial analyses will be conducted under the assumption of MCAR/MAR (ignorable missing). Sensitivity analyses using multiple imputation and pattern mixture models will be used to assess the robustness of the model assumptions. The analysis of specific aim 2 proposes to use a modification of the ITT principle. Justification for this is that it is a mechanistic aim with blinded examiners. We are interested in quantifying the effects of washing as clearly (and perhaps ideally) this is an early phase trial. In Aim 3, the clinical outcomes will be assessed using the traditional ITT definition to provide a more realistic measure of the effect size for planning subsequent studies.

Protocol Addendum:

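### The SpO2 part of the Aim 3 hypoxemia outcome mixes lung function with oxygen support, so the sign of its mean or AUC cannot be read as better or worse oxygenation

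*Combined protocol and SAP*

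**What the plan says.** - **Analysis.** Statistical Considerations, Aim 3 paragraph: "Serial measurements (oxygen saturation) will be analyzed using longitudinal summary statistics (e.g., AUC, mean value". The text does not say which readings count (on oxygen, on room air, or all), over what period, or whether the AUC is divided by time.
- **Outcomes.** Outcome Measures, Specific Aim 3, lists "evaluations of hypoxemia (SpO_2 , PaO_2/FiO_2), duration of oxygen supplementation" among the secondary outcomes.
- **Oxygen rule.** Other aspects of care: "Non-intubated patients will undergo standard titration of oxygen twice daily (at 0700 and 1900, +/- 2 hours"; and "Patients saturating 92% or greater on room air will not receive supplemental oxygen, unless specifically requested by the primary service". Evaluation for titration continues "until liberation from oxygen therapy for 24 hours, hospital day 28, or hospital discharge, whichever comes first". The Table of Events confirms that titration applies to extubated patients only.
- **Hypothesis.** Aim 3a expects "shorter duration of mechanical ventilation, oxygen supplementation, and ICU stay; improved oxygenation; and improved organ function".
- **Status.** The same Aim 3 paragraph states: "It should be noted that the intermediate clinical outcomes are not being powered for in this study". It adds that the estimates will inform the design of later trials.

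**The concern.** SpO2 measures lung function only when inspired oxygen is the same, or is accounted for. Here the protocol itself changes inspired oxygen as patients recover. A patient whose lungs have recovered is on room air and may sit a little above 92%. A patient who has not recovered stays on oxygen and may sit higher because of it. A summary that pools both kinds of reading can rank the second patient above the first.

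Improved oxygenation and shorter oxygen supplementation are both named benefits under Aim 3a. If washing shortens time on oxygen, that same benefit can pull mean SpO2 down. What is at stake is the SpO2 estimate handed to the designers of the next trial: its sign would not tell them whether oxygenation improved.

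**Working it through.** The plan gives no figure for this endpoint to reproduce. Its sample size of 78 per group is for the Aim 2a biomarkers and does not enter here.

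**Inputs from the documents:** checks every 12 hours (0700 and 1900); no oxygen at 92% or more on room air; titration checks end after 24 hours off oxygen, at hospital day 28 or at discharge.

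**Assumptions, not in the documents:** a 5-day window (10 readings); patient A on oxygen for 1 day (2 readings) and patient B for 4 days (8 readings); the same saturation *on* while on oxygen and *ra* on room air for both; FiO2 of 0.28 to 0.40 on oxygen.

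**1. Mean SpO2, fixed window**

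Mean A = (2·on + 8·ra)/10; mean B = (8·on + 2·ra)/10; A − B = 0.6 × (ra − on).

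| On oxygen | Room air | Mean A | Mean B | A − B |
|---|---|---|---|---|
| 98 | 92 | 93.2 | 96.8 | -3.6 |
| 96 | 93 | 93.6 | 95.4 | -1.8 |
| 96 | 95 | 95.2 | 95.8 | -0.6 |
| 92 | 92 | 92.0 | 92.0 | 0.0 |
| 94 | 95 | 94.8 | 94.2 | +0.6 |
| 92 | 97 | 96.0 | 93.0 | +3.0 |

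Patient A recovers sooner in every row. The sign depends only on whether saturation on oxygen is above or below saturation on room air.

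**2. AUC, same fixed window** (trapezoid, 12-hour steps, 96% on oxygen and 93% on room air)

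AUC = 12 × (sum of readings − half of first plus last).
A: 12 × (936 − 94.5) = 10,098. B: 12 × (954 − 94.5) = 10,314. Difference: -216 %-hours, the same direction as the mean.

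**3. Group level**

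A simulation took mean time on oxygen as 2 days (washed) and 3 days (control) over the 5-day window. Mean SpO2, washed minus control:

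| On oxygen / room air | Difference |
|---|---|
| 97 / 94 | -0.57 |
| 96 / 94 | -0.38 |
| 95 / 95 | 0.00 |
| 94 / 96 | +0.38 |

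A hand check agrees. One day fewer on oxygen moves 2 of 10 readings, so the difference is about 0.2 × (ra − on), or -0.6, -0.4, 0 and +0.4.

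**4. AUC if readings stop with the titration checks** (the documents do not say that they do)

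Let readings end 24 hours after the first room-air reading: 5 readings for A and 11 for B. At 96% throughout, AUC for A is 4 × 12 × 96 = 4,608 and for B 10 × 12 × 96 = 11,520. At 94% on oxygen and 96% on room air they are 4,572 and 11,340. B is larger because B is followed longer, even when saturations are equal or better on room air. A mean is free of this effect: at equal saturations both patients score 96.0.

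**5. SpO2/FiO2 instead**

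Room air at 93%: 93/0.21 = 443. On oxygen at 96%: 96/0.28 = 343, 96/0.35 = 274, 96/0.40 = 240. The extremes of the assumed range keep the order: the lowest room-air score is 92/0.21 = 438 and the highest on-oxygen score is 98/0.28 = 350. In the simulation, with FiO2 0.35 on oxygen, the difference favours the earlier-weaned group in all four settings (+33 to +36).

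**The case against.** **Hypoxemia is not judged on SpO2 alone.** This stands. PaO2/FiO2 already accounts for inspired oxygen, and time on oxygen is its own outcome, so earlier weaning would show there. A reader might infer that the whole hypoxemia outcome is mis-scored; the outcome list does not support that. SpO2 is nevertheless the only serial measure that the Aim 3 analysis text names, and the Table of Events schedules no blood gas.

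**The summaries are only examples, and room-air readings might be meant.** It is true that the text leaves this open. But both named examples share the fault when readings on and off oxygen are pooled, and nothing restricts which readings are used.

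**The oxygen rule has limits.** It covers non-intubated patients and allows exceptions at the primary service's request, so readings during ventilation fall outside it. That narrows the effect. The exceptions do not remove it: the clinical team is unblinded, and oxygen given on request can raise SpO2 without better lungs.

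**The AUC effect in step 4 needs an unstated link.** This stands. The stopping rule is written for titration checks, and no text ties SpO2 outcome readings to it. An AUC divided by time would also avoid the effect.

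**The outcome is exploratory and unpowered.** This stands, and it limits the weight of the point.

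**Conclusion.** The point holds for the SpO2 component of the Aim 3 hypoxemia outcome. As written, its mean or AUC combines lung function with oxygen support, and its sign cannot be read as better or worse oxygenation. For the assumed pair of patients the difference in mean runs from -3.6 to +3.0 points. It is negative whenever saturation on oxygen exceeds saturation on room air. These figures rest on assumed saturations, durations and window, since the documents give none for this outcome.

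A reader might go further and infer that the trial would report worse oxygenation for the better arm. The documents do not support that. Reversal is possible but not certain, and two other outcomes would be read beside this one. Nor is it established that AUC rewards longer time on oxygen through longer follow-up; that holds only if readings stop with the titration checks and the AUC is not divided by time.

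The trial's main conclusions are unaffected. The gain from a correction is an interpretable estimate for planning later trials.

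**What to change.** Amend Outcome Measures (Specific Aim 3) and the Aim 3 paragraph of Statistical Considerations:

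1. Replace unadjusted SpO2 with SpO2/FiO2, taken at the existing 0700 and 1900 checks in extubated patients, and at matching times with the set FiO2 while ventilated.
2. Summarise it as a time-averaged value over one fixed window for everyone, for example Study Days 1-5, the period already used for the daily ARDS/TRALI/TACO assessment.
3. State the rule for death and for discharge before the window ends.
4. Drop any AUC that is not divided by time.
5. Interpret the result beside PaO2/FiO2 and duration of oxygen supplementation.

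Room-air SpO2 alone should not be the main measure, because intubated patients cannot supply it and the sickest would drop out.

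**Cost.** Analysis-plan wording, and FiO2 or oxygen flow recorded with each reading. FiO2 on nasal cannula is approximate and needs one standard conversion. Titration checks end 24 hours after liberation, so later readings within the window would have to come from routine vital signs, or the reading alone be continued. No clinical rule and no sample size changes.
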